### **2.3. Study Endpoints**

Safety assessments are the primary focus for the final CSR.

#### **2.3.1. Safety Endpoints**

Safety endpoints to be evaluated include exposure, incidence of treatment-emergent adverse events (TEAEs), serious adverse events (SAEs) including infusion-associated reactions (IARs), AEs leading to discontinuation from the study, TEAEs leading to discontinuation of study drug, TEAEs leading to death, frequency and severity of immediate and late IARs, and abnormalities noted in other safety assessments (eg, clinical laboratory tests, electrocardiograms (ECGs), vital signs).

### **2.3.2. Efficacy Endpoints**

The protocol does not designate any particular endpoint as the ‘primary’ for the OLE study. For purposes of the CSR, efficacy endpoints will be split into two groups, as (1) main efficacy endpoints and (2) supportive efficacy endpoints.

#### **2.3.2.1. Main Efficacy Endpoints**

- Change from baseline in 6-minute walk distance (6MWD) which is the distance walked (in meters) in the 6MWT
- Change from baseline in sitting FVC (% predicted)

Note: The predicted FVC values will be age-adjusted based on the subject’s age at the assessment visit.

- Change from baseline in the manual muscle test (MMT) score for the lower extremities
- Change from baseline in the total score for the Patient-reported Outcomes Measurement Information System (PROMIS®) – Physical Function
- Change from baseline in the total score for the PROMIS – Fatigue
- Change from baseline in the total score for the Gait, Stairs, Gowers’ maneuver, and Chair test (GSGC)

#### **2.3.2.2. Supportive Efficacy Endpoints**

Supportive efficacy endpoints include:

- Change from baseline in % predicted 6MWD (PP6MWD), where the predicted values are calculated using [Enright and Sherrill 1998](#) reference equations
- Change from baseline in the following variables related to motor function:
  - time to complete the 10-meter walk (ie, assessment of gait) of the GSGC test
  - time to complete the 4-stair climb of the GSGC test
  - time to complete the Gowers’ maneuver of the GSGC test
  - time to rise from a chair as part of the GSGC test
  - time to complete the Timed Up and Go (TUG) test
- Change from baseline in the following variables related to muscle strength:
  - MMT score for the upper extremities
  - MMT total score (upper and lower extremities combined)
  - Proximal muscles MMT score
  - Quantitative muscle test (QMT) value (kg) for the upper extremities
  - QMT value (kg) for the lower extremities

- QMT total value (kg) (upper and lower extremities combined)
- Change from baseline in the following variables from patient-reported outcome (PRO) measures:
  - Total score for the PROMIS – Dyspnea
  - Total score for the PROMIS – Upper extremities
  - Total score for the Rasch-built Pompe-specific Activity (R-PAct) Scale
- European Quality of Life (EuroQol)-5 Dimensions 5 Response Levels (EQ-5D-5L) health status which includes the categorical dimensional levels and the quantitative Visual Analogue Scale (EQ-VAS) score. That is:
  - Absolute value and categorical change in the levels of each EQ-5D-5L dimensional measure
  - Change from baseline in the EQ-VAS score
- Actual value of the subject's functional status (improving, stable, or declining) pertaining to the effects of study drug in the following areas of life, as measured by the Subject's Global Impression of Change (SGIC):
  - overall physical wellbeing
  - effort of breathing
  - muscle strength
  - muscle function
  - ability to move around
  - activities of daily living
  - energy level
  - level of muscular pain
- Actual value of the subject's functional status (improving, stable, or declining), as measured by the Physician's Global Impression of Change (PGIC)
- Change from baseline in the following measures of pulmonary function, as follows:
  - Sitting slow vital capacity (SVC) (% predicted)
  - Maximum vital capacity (VC) (% predicted), where maximum VC is defined as the larger of the sitting FVC and the sitting SVC
  - Maximal inspiratory pressure (MIP) (% predicted)
  - Maximal expiratory pressure (MEP) (% predicted)
  - Sniff nasal inspiratory pressure (SNIP) (% predicted)

### **2.3.3. Pharmacodynamic Endpoints**

Pharmacodynamic (PD) variables are:

- Change from baseline in serum creatine kinase (CK) level
- Change from baseline in urinary hexose tetrasaccharide (Hex4) level

### **2.3.4. Immunogenicity Endpoints**

Immunogenicity (IMG) variables are:

- Total anti-drug antibodies (ADAs), including titers
- Neutralizing antibodies (Nabs):
  - Inhibition of recombinant human acid  $\alpha$ -glucosidase (rhGAA) binding to cation-independent mannose-6-phosphate receptor (CI-MPR)
  - Inhibition of rhGAA-mediated hydrolysis of 4-MU-glucoside
  - Inhibition of rhGAA-mediated hydrolysis of glycogen
- Anti-rhGAA cross-reactive with alglucosidase alfa
- Anti-rhGAA-specific Immunoglobulin E (IgE)

### **3. STUDY DESIGN**

#### **3.1. Summary of Study Design**

This is a multicenter, international, OLE study of ATB200/AT2221 (heretofore referred to as cipaglucosidase alfa/miglustat) in adult subjects with late-onset Pompe disease (LOPD) who completed the randomized double-blind Study ATB200-03. Study ATB200-07 consists of a treatment period that lasts until 31 December 2024 or until study termination by the sponsor, and it includes a 30-day safety follow-up period for the end of study (EOS) or early termination (ET) assessments.

All subjects in Study ATB200-07 are to be treated with cipaglucosidase alfa/miglustat every 2 weeks. Subjects who previously received alglucosidase alfa/placebo in Study ATB200-03 were switched to cipaglucosidase alfa/miglustat in Study ATB200-07, and subjects who received cipaglucosidase alfa/miglustat in Study ATB200-03 continued on cipaglucosidase alfa/miglustat in Study ATB200-07. The first infusion visit in this study was to be scheduled approximately 2 weeks after the last visit in Study ATB200-03 in an effort to ensure continued administration of study drug on the same schedule with no gap between studies. The end of study assessment in Study ATB200-03 will be considered the baseline assessment in Study ATB200-07, as described in Section 4.4.2.

#### **3.2. Definition of Study Drugs**

The dose of miglustat is 260 mg ( $4 \times 65$ -mg oral capsules) for subjects weighing  $\geq 50$  kg, or 195 mg ( $3 \times 65$ -mg oral capsules) for subjects weighing  $\geq 40$  kg to  $< 50$  kg. Miglustat is administered orally and is followed approximately 1 hour later by IV infusion of 20 mg/kg cipaglucosidase alfa (administered over a 4-hour period). Subjects are required to fast at least 2 hours before and 2 hours after administration of miglustat.

#### **3.3. Sample Size Considerations**

The maximum sample size for this study was based on the number of subjects expected to complete Study ATB200-03, estimated to be approximately 110 subjects at up to approximately 59 sites globally.

#### **3.4. Randomization and Stratification**

This is an open-label extension study, and it is uncontrolled. There is no randomization or stratification.

#### **3.5. Clinical Assessments**

Study assessments were to be performed in accordance with the Schedule of Assessments of the ATB200-07 study protocol.

Safety assessments including clinical lab tests (chemistry, hematology, urinalysis), brief physical examination (BPE), and vital signs were to be performed at Baseline Visit (for subjects who did not complete Week 52 in Study ATB200-03), and at Weeks 2, 4, 6, 12, 26, and then every 26 weeks thereafter. Assessments of Hex4 were also to be performed at Baseline Visit (for subjects who did not complete Week 52 in Study ATB200-03), and at Weeks 2, 4, 6, 12, 26, and

then every 26 weeks thereafter. Assessments of efficacy and ECG were to be performed at Baseline Visit (for subjects who did not complete Week 52 in Study ATB200-03), and at Weeks 12, 26, and then every 26 weeks thereafter.

### **3.6. Impact of COVID-19 Pandemic**

During the conduct of the study, the pandemic caused by the SARS-CoV-2 virus (COVID-19) emerged and impeded the conduct of site visits and laboratory testing due to quarantines, travel restrictions, and risk of infection. This could result in some subjects experiencing delayed visits, missed infusions, missed assessments, and early withdrawals from the study.

Missed assessment and infusion visits due to COVID-19 related reasons were to be recorded as protocol deviations in the electronic data capture (EDC) and the reasons attributed to COVID-19. Infusions that were missed near the scheduled assessment visits (particularly at Weeks 12, 26, and every 26 weeks after Week 26) were to be examined on a case-by-case basis to determine whether catch-up infusions were needed, and if so, how many catch-up infusions were needed, prior to rescheduling the visits to perform make-up assessments.

### **3.7. Interim Analysis**

This is an OLE study, and the protocol allowed for an informal interim analysis to be conducted for purposes of writing an interim clinical study report.

## **4. GENERAL CONSIDERATIONS FOR DATA ANALYSES AND HANDLING**

### **4.1. Analysis Populations**

#### **4.1.1. OLE Enrolled Subjects**

The open-label extension enrolled subjects (OLE-ES) includes all subjects who satisfied the eligibility requirements (based on the inclusion and exclusion criteria) and entered the OLE Study ATB200-07.

The OLE-ES population will be used for reporting protocol deviations and for subject accounting purposes.

#### **4.1.2. OLE Safety Population**

The open-label extension safety population (OLE-SAF) includes all subjects who took at least one dose of cipaglucosidase alfa/miglustat combination treatment in Study ATB200-07.

The OLE-SAF population will be used for reporting all safety data, demographic and baseline characteristics, disease characteristics, medical history, medications and nondrug therapies, exposure, and compliance.

#### **4.1.3. Full Analysis Set**

The Full Analysis Set (FAS) includes all subjects who entered the OLE Study ATB200-07 who had both a valid baseline and at least one post-baseline assessment, for at least 1 of the main efficacy endpoints (6MWD, FVC, MMT-lower extremities, PROMIS-Physical Function, PROMIS-Fatigue, and GSGC).

The FAS population will be used for reporting all efficacy and PD data.

## **4.2. Presentation by Treatment Group**

Presentation of treatment group in the analysis outputs for the CSR will be as follows:

1. Cipaglucosidase alfa/miglustat—Cipaglucosidase alfa/miglustat: subjects treated with cipaglucosidase alfa/miglustat in Study ATB200-03 and continued cipaglucosidase alfa/miglustat in Study ATB200-07.
2. Alglucosidase alfa/placebo—Cipaglucosidase alfa/miglustat: subjects treated with alglucosidase alfa/placebo in Study ATB200-03 and switched to cipaglucosidase alfa/miglustat in Study ATB200-07.

Where appropriate, these 2 treatment groups will be presented together with the overall treatment group (which combines [1] and [2]) so that all 3 treatment groups are displayed in the results presentation.

## 4.3. Subgroups

### 4.3.1. Planned Subgroups of Interest

At the time of entering Study ATB200-07, all subjects had at least one year of treatment with enzyme replacement therapy (ERT). Nonetheless, the previous ERT status of the subjects prior to entering the pivotal Study ATB200-03 remains a subgroup of interest in the analysis of the standalone data from Study ATB200-07.

The planned subgroups of interest Study ATB200-07 are the prior ERT status groups, which are defined as follows:

- ERT-experienced: subjects in the OLE study who had been previously treated with ERT prior to their participation in the randomized double-blind Study ATB200-03
- Previously ERT-naïve: subjects in the OLE study who had not been previously treated with ERT prior to their participation in the randomized double-blind Study ATB200-03

In particular, the 6 main efficacy endpoints specified in Section 2.3.2.1 as well as the % predicted 6MWD among others, will be presented by the prior ERT status subgroups.

### 4.3.2. Other Subsets of Subjects

Additionally, the following subsets of subjects will be used for the analyses indicated below, unless otherwise stated. The baseline indicated below refers to the baseline result in Study ATB200-07.

- Baseline % predicted FVC categories: < 85%, ≥ 85%.  
This will be used to summarize % predicted FVC overall and by ERT status.

## 4.4. Data Handling

### 4.4.1. Study Day

For the purposes of analysis, the date of first dose of study drug (First Dose Date) in ATB200-07 is designated as Day 1 and it will serve as the reference start date. The following relative days are considered:

- Total duration of treatment (ie, exposure) will be calculated as: (last dose date prior to data cutoff – first dose date) + 1.
- If the date of interest occurs on or after the first dose date, then study day will be calculated as: (date of interest – first dose date) + 1.
- If the date of interest occurs prior to the first dose date, then study day will be calculated as: (date of interest – first dose date).

#### **4.4.2. Baseline Definition**

In general, baseline is defined as the last available value on or prior to the administration of the first dose of study drug in Study ATB200-07. This is the case for all endpoints unless otherwise specified.

Note that:

- For subjects who completed Week 52 in Study ATB200-03, the results from the last visit in Study ATB200-03 were to serve as baseline values in ATB200-07. These data may already be available in the EDC system for Study ATB200-07.
- If the result from Week 52 of Study ATB200-03 was missing, then that assessment was to be performed at the Baseline Visit in Study ATB200-07 on or before the first dose date. For the 6MWD and % predicted 6MWD, 2 such assessments may be performed: if 2 assessments were performed, then the average is to serve as the baseline result; otherwise, the single value is to serve as the baseline result.
- If a subject had a change in the use of an assistive device that was used to perform the 6MWD during the Study ATB200-03, then the 6MWD was repeated in ATB200-07 (on or prior to the first dose date) to re-establish the baseline result.
- For all other endpoints (apart from the 6MWD and % predicted 6MWD), if there is more than one baseline value for a subject, the latest value (ie, last in chronological order) will be used.

#### **4.4.3. Change and Percent Change from Baseline**

Change from baseline is calculated as: Value at a visit – Baseline value.

Percent change from baseline is calculated as:

$100 * (\text{Value at a visit} - \text{Baseline value}) / \text{Baseline value}$ .

#### **4.4.4. Baseline Age**

Baseline age (years) for subjects in ATB200-07 is calculated as:

$\text{FLOOR} ([\text{date of informed consent in ATB200-07} - \text{date of birth}] / 365.25)$ ,

where the FLOOR ( ) function returns the integer part of the result.

### **4.5. Analysis Visit Windows**

Analysis visit windows will be used for all by-visit analyses.

#### **4.5.1. Visit Windows for By-visit Safety Analysis**

By-visit safety endpoints including clinical laboratory and vital signs, BPE, and ECG as well as PD will be analyzed based on the by-visit safety windows in [Table 2](#).

**Table 2: Visit Windows for By-visit Safety Data**

| Study Visit             | Target Day | Analysis Visit Window |
|-------------------------|------------|-----------------------|
| Baseline [a] | 1          | Baseline              |
| Week 2                  | 15         | Day 2 – Day 22        |
| Week 4                  | 29         | Day 23 – Day 36       |
| Week 6                  | 43         | Day 37 – Day 64       |
| Week 12                 | 85         | Day 65 – Day 134      |
| Week 26                 | 183        | Day 135 – Day 274     |
| Week 52                 | 365        | Day 275 – Day 456     |
| Week 78                 | 547        | Day 457 – Day 638     |
| Week 104                | 729        | Day 639 – Day 820     |
| Week 130                | 911        | Day 821 – Day 1002    |
| Week 156                | 1093       | Day 1003 – Day 1184   |
| Week 182                | 1275       | Day 1185 – Day 1366   |
| Week 208                | 1457       | Day 1367 – Day 1548   |
| Week 234                | 1639       | > Day 1548            |

Abbreviation: 6MWT = six-minute walk test

[a] In general, baseline is derived as the last assessment on or prior to the first dose date in Study ATB200-07. For most subjects, the baseline value will be the assessment from Week 52 in ATB200-03. For subjects who did not complete Week 52 in Study ATB200-03, baseline assessments are to be performed at the Baseline visit. If a subject has a change in the use of an assistive device that was used to perform the 6MWT during Study ATB200-03, then the 6MWT is to be repeated at the Day 1 Visit.

#### 4.5.2. Visit Windows for Efficacy Analysis

Efficacy endpoints and PRO measures will be analyzed based on the efficacy visit windows in [Table 3](#).

**Table 3: Visit Windows for Efficacy and Patient-reported Outcome Data**

| Week                    | Target Day | Analysis Visit Window |
|-------------------------|------------|-----------------------|
| Baseline [a] | 1          | Baseline              |
| Week 12                 | 85         | Day 2 – Day 134       |
| Week 26                 | 183        | Day 135 – Day 274     |
| Week 52                 | 365        | Day 275 – Day 456     |
| Week 78                 | 547        | Day 457 – Day 638     |
| Week 104                | 729        | Day 639 – Day 820     |
| Week 130                | 911        | Day 821 – Day 1002    |
| Week 156                | 1093       | Day 1003 – Day 1184   |

**Table 3: Visit Windows for Efficacy and Patient-reported Outcome Data (Continued)**

| Week     | Target Day | Analysis Visit Window |
|----------|------------|-----------------------|
| Week 182 | 1275       | Day 1185 – Day 1366   |
| Week 208 | 1457       | Day 1367 – Day 1548   |
| Week 234 | 1639       | > Day 1548            |

Abbreviation: 6MWT = six-minute walk test

[a] In general, baseline is derived as the last assessment on or prior to the first dose date in Study ATB200-07. For most subjects, the baseline value will be the assessment from Week 52 in Study ATB200-03. For subjects who did not complete Week 52 in Study ATB200-03, baseline assessments are to be performed at the Baseline Visit. If a subject has a change in the use of an assistive device that was used to perform the 6MWT during ATB200-03, then the 6MWT is to be repeated at the Day 1 Visit.

#### **4.5.3. Multiple Assessments in a Visit Window**

For the CSR, the usual windowing rules for handling multiple assessments will be followed for both safety and efficacy by-visit data. No active rule for reassigning/remapping missing visits due to COVID-19 related reasons to address delayed visits will be implemented.

If multiple assessments (from both scheduled and unscheduled visits) occur in the same visit window, the value closest to the planned target visit day will be used for that visit. If 2 values are equidistant from the target day or occur on the same day but at different times, the last assessment in chronological order will be used. If the 2 assessments have the same date and time, then the larger value will be used.

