## **8.2. Duration of Study**

The study will consist of a treatment period that lasts until one of the following conditions apply:

- the product is approved and commercialized for use in the investigational study population, or
- cipaglucosidase alfa/miglustat is rejected by the regulatory authority in the subject's local country as an approved treatment for Pompe disease, or
- the sponsor decides to continue to provide cipaglucosidase alfa/miglustat via a post-trial access mechanism, or
- the subject is withdrawn or withdraws consent, or
- the sponsor decides to end the study.

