## 1. INTRODUCTION

This statistical analysis plan (SAP) describes the planned data analyses and the outputs to be included in the final clinical study report (CSR) for the standalone open-label extension (OLE) Study ATB200-07. The SAP is based on Amendment 3 of the Protocol for Study ATB200-07 dated 10 December 2024.

This final SAP describes the analyses that will be performed for the final CSR for the standalone Study ATB200-07 based on a data cutoff date of 31 December 2024. All data collected through the cutoff date will be reported as summary tables and/or listings.

This SAP has been developed in accordance with Good Clinical Practice (GCP), International Council on Harmonisation (ICH) guideline E9 (Statistical Principles for Clinical Trials), and Amicus standard operating procedure (SOP) ATCRA-SOP-AT-008.

The analyses and statistical methods specified in the final SAP supersede those described in the study protocol.

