## **5.3. Exposure and Treatment Compliance**

Study drug exposure will be summarized for the cipaglucosidase alfa/miglustat combination treatment rather than separately for cipaglucosidase alfa and miglustat. All analyses will be based on the exposure during Study ATB200-07 only.

Analyses will be presented by treatment groups Cipaglucosidase alfa/miglustat–Cipaglucosidase alfa/miglustat, Alglucosidase alfa/placebo–Cipaglucosidase alfa/miglustat, and overall, as defined in Section 4.2. The duration of treatment (ie, extent of exposure), in months, will be calculated as (date of last dose in ATB200-07 – date of first dose in ATB200-07 + 1) / 30.4, and summarized using descriptive statistics (n, mean, SD, median, minimum, and maximum).

In addition, the duration of treatment will be categorized into the exposure intervals below and summarized using number and percentages of subjects:

≤ 3 months, > 3 to ≤ 6 months, > 6 to ≤ 9 months, > 9 to ≤ 12 months, > 12 to ≤ 18 months, > 18 to ≤ 24 months, > 24 to ≤ 36 months, > 36 to ≤ 48 months, > 48 months to ≤ 60 months, and > 60 months.

Additionally, a summary of the duration of treatment (exposure) will be provided by prior ERT status.

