### **7.3. Clinical Safety Laboratory Data**

Laboratory data will be presented using the Système International (SI) unit. Descriptive statistics (n, mean, SD, median, Q1, Q3, minimum, and maximum) will be presented for the absolute visit values, change from baseline, and percent change from baseline to post-baseline visits by treatment group and overall, and by visit, starting at the Baseline visit. Summaries will be presented by the specific lab parameters within the domains of clinical chemistry, hematology, and urinalysis.

Line plots of mean  $\pm$  SE of the change from baseline and percent change from baseline over time will be provided for alanine aminotransferase (ALT) and aspartate aminotransferase (AST) by treatment group and overall. Similar line plots will also be provided by prior ERT status.

Additionally, a summary of the number and percentage of subjects with treatment-emergent or newly-occurring laboratory values that meet pre-defined limits of change (PDLC) at any post-baseline visit will be presented by treatment group and overall. The PDLC criteria are provided in [Table 4](#). If a subject has even 1 post-baseline value that meets the PDLC criteria for any particular lab parameter, then all values of that parameter for that subject will be listed.

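### The last visit window in the SAP (Week 234) has no upper day limit, so a Week 260 assessment would drop out of the by-visit summaries or appear as Week 234

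*SAP*

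**What the plan says.** SAP 4.5 gives the windows full scope: "Analysis visit windows will be used for all by-visit analyses". Table 2 covers by-visit safety and pharmacodynamic data; Table 3 covers efficacy and patient-reported outcomes. In both, the second-to-last row is Week 208 (target Day 1457, "Day 1367 – Day 1548"). The last is Week 234 (target Day 1639), defined only as later than Day 1548.

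SAP 4.5.3 keeps one value per window. Where there are several, scheduled or unscheduled, "the value closest to the planned target visit day will be used for that visit", and ties go to the later assessment. The same section rules out remapping of visits missed because of COVID-19.

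SAP 3.5 schedules efficacy and ECG assessments at baseline "and at Weeks 12, 26, and then every 26 weeks thereafter", with no last visit named. Protocol Table 4 likewise sets no stop at Week 234. SAP 5.3 lists exposure categories that end with "and > 60 months".

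**The concern.** Every other post-baseline window closes at the midpoint to the next target, so each row holds values close to its label. The last row does not, and there is no row for the next scheduled visit, Week 260. Combined with the closest-to-target rule, this has one of two effects on a Week 260 value. It is discarded when a nearer value exists, or it is reported under a label half a year too early.

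The values at risk are the latest in the study, from the earliest-dosed subjects, and the study's stated purpose is long-term safety and efficacy. The outputs exposed are the by-visit efficacy, patient-reported outcome, CK and Hex4, laboratory, vital-sign, physical-examination and ECG summaries, and the mean-change line plots.

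**Working it through.** **Inputs.** Target days, windows and the selection rule are from SAP Tables 2 and 3 and SAP 4.5.3. The 26-week schedule is from SAP 3.5 and Protocol Table 4, the cutoff of 31 December 2024 from SAP 1, and the month length of 30.4 days from SAP 5.3. The original protocol date, 25 March 2019, is from the protocol's document history.

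**1. Reproduce the SAP's windows.** Target day = 7 × week + 1. Upper limit = midpoint of adjacent targets, rounded down.
- Week 208: 7 × 208 + 1 = 1457. Week 234: 7 × 234 + 1 = 1639. Midpoint (1457 + 1639)/2 = 1548, as stated.
- All 10 target days and all 9 closed upper limits in Table 3 reproduce, as do the Table 2 limits of Day 22, 36 and 64.
- The largest distance from target in any closed window is 91 days (for example 1548 − 1457).

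**2. Extend the same rule.**
- Week 260: 7 × 260 + 1 = Day 1821. Week 286: 7 × 286 + 1 = Day 2003.
- Week 234 would close at (1639 + 1821)/2 = Day 1730.
- Week 260 would run from Day 1731 to (1821 + 2003)/2 = Day 1912.

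**3. Apply SAP 4.5.3 to the open window.**
- A value at Day 1549 to 1730 is at most 91 days from Day 1639 (1730 − 1639 = 91).
- A value at Day 1731 or later is at least 92 days away (1731 − 1639 = 92).
- The later value can therefore never win or tie. All 182 × 182 pairs of one value from Day 1549–1730 and one from Day 1731–1912 were checked, and the later value was chosen in none.
- With no value at Day 1549–1730, the earliest value after Day 1730 is shown as Week 234. For an on-schedule Week 260 visit the error is 1821 − 1639 = 182 days, twice the 91-day maximum.

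**4. Who can be affected by the cutoff.** Latest first-dose date for each study day to fall on or before 31 December 2024:

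| Study day | Meaning | First dose no later than |
|---|---|---|
| 1731 | first day beyond a closed Week 234 window | 6 April 2020 |
| 1818 | Week 260 visit, 3 days early | 10 January 2020 |
| 1821 | Week 260 on target | 7 January 2020 |
| 1825 | first day over 60 × 30.4 = 1,824 days of exposure | 3 January 2020 |
| 1913 | first day beyond a Week 260 window | 7 October 2019 |

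A first dose on the original protocol date, an extreme bound, gives Day 2109 at the cutoff. That is short of Week 312 (312 × 7 + 1 = Day 2185).

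**5. Share of a subject's record.** Post-baseline efficacy visits are Weeks 12, 26, 52, 78, 104, 130, 156, 182, 208, 234 and 260, so 11 in all. A subject with both late values loses the last of 11 from the by-visit tables.

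**The case against.** The mechanics are not in dispute; the case against is about materiality.

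- **Possibly nobody is affected.** First-dose dates are not given. Under Protocol 8.2 treatment ends once "the product is approved and commercialized for use in the investigational study population", and Protocol 6.1 reports approvals in the EU, Great Britain, the US and elsewhere, so early subjects may have left before Day 1821. The top exposure category is an open bin that proves no one is in it, and it counts dosing rather than assessments. This stands: the impact is conditional. The SAP nevertheless foresees the follow-up in one table and gives it no row in another. Off-schedule or early-termination values from Day 1731 meet the same fate, which needs only a first dose by 6 April 2020.
- **Pooling a sparse tail may have been intended.** Nothing labels the row as Week 234 or later, and it carries a single target day. Even a pooled row would not justify a rule that always discards the later value.
- **Consequences are bounded.** The analysis is descriptive, safety is the main focus, and SAP 1 promises that "All data collected through the cutoff date will be reported as summary tables and/or listings". Limit-of-change summaries count subjects whose values "meet pre-defined limits of change (PDLC) at any post-baseline visit", so they keep these data. This stands, and it limits the point to by-visit outputs.
- **The CSR addendum might recover the values.** It does not. Protocol Appendix 1, 15.3.4, restricts the addendum to data collected after database lock, with no integration of earlier data.
- **A conditional Week 286 row depends on the data.** Only whether it is printed does. Its limits follow from the existing rule and can be fixed in advance.

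**Conclusion.** The concern holds. As written, the SAP removes a Week 260 value from the by-visit rows when the subject has any value at Day 1549 to 1730. Otherwise it tabulates that value as Week 234, 182 days off target, unless another value after Day 1730 lies closer to Day 1639. No other SAP rule prevents this.

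The number of subjects affected cannot be derived from the documents and may be zero. The result assumes that at least one subject was first dosed early enough (by 7 to 10 January 2020 for a Week 260 visit on target or up to 3 days early, or by 6 April 2020 for any value from Day 1731) and was still being assessed. Listings, TEAE and IAR summaries, exposure and limit-of-change summaries are not affected. The change should be made, because a stated rule would misreport the longest follow-up, but no formal inference depends on it.

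**What to change.** In SAP Tables 2 and 3:

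- Close Week 234 at Day 1549 to Day 1730.
- Add Week 260, target Day 1821, Day 1731 to Day 1912.
- Only if a subject has data after Day 1912, add a final row for Week 286, target Day 2003, Day 1913 and later. No further row can be needed, since Day 2109 is the latest possible study day at the cutoff.

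SAP 4.5.3 can stay as it is; the selection rule works once the windows are closed.

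The cost is one extra row per table, or two if data extend past Day 1912. The last rows may rest on few subjects, but n is reported at each visit, so this will be visible. If no subject has data after Day 1730, no result changes.
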